	Data will be used for scientific presentations, publications, and in future grant applications.					
	e. Consent . Will consent be obtained now from subjects for the secondary use, banking and/or future sharing?					
X	No Yes	→ If yes, be sure to include the information about this consent process in the consent form (if there is one) and in the answers to the consent questions in Section 8.				
f.	f. Withdrawal . Will subjects be able to withdraw their data/specimens from secondary use, banking or sharing?					
Χ	No					
	Yes	ightarrow If yes, describe how, and whether there are any limitations on withdrawal.				
		Example: data can be withdrawn from the repository but cannot be retrieved after they are released.				
g	g. Agreements for sharing or release . Confirm by checking the box that the sharing or release will comply with UW (and, if applicable, UW Medicine) policies that require a formal agreement with the recipient for release of data or specimens to individuals or entities other than federal databases.					

Data Use Agreements or Gatekeeping forms are used for data; Material Transfer Agreements are used for specimens (or specimens plus data). Do not attach any template agreement forms; the IRB neither reviews nor approves them

X Confirmed

5.11 Communication with subjects during the study. Describe the types of communication (if any) the research team will have with already-enrolled subjects during the study. Provide a description instead of the actual materials themselves.

Examples: email, texts, phone, or letter reminders about appointments or about returning study materials such as a questionnaire; requests to confirm contact information.

Participants enrolled in the study will be contacted via email, phone, or text (as requested) about appointments for study procedures and to answer questions or provide reminders about study materials.

5.12 Future contact with subjects. Is there a plan to retain any contact information for subjects so that they can be contacted in the future?

No X Yes

→ If yes, describe the purpose of the future contact, and whether use of the contact information will be limited to the study team; if not, describe who else could be provided with the contact information. Describe the criteria for approving requests for the information.

Examples: inform subjects about other studies; ask subjects for additional information or medical record access that is not currently part of the study proposed in this application; obtain another sample.

Contact information will be limited to the research team, and be used to either obtain additional information, or to inform subjects about other studies if they elect to be contacted.

5.13 Alternatives to participation. Are there any alternative procedures or treatments that might be advantageous to the subjects?

If there are no alternative procedures or treatments, select "No". Examples of advantageous alternatives: earning extra class credit in some time-equivalent way other than research participation; obtaining supportive care or a standard clinical treatment from a health care provider instead of participating in research with an experimental drug.

 \rightarrow If yes, describe the alternatives.

5.14 Upload to *Zipline* all data collection forms (if any) that will be directly used by or with the subjects, and any scripts/talking points that will be used to collect the data. Do not include data collection forms that will be used to abstract data from other sources (such as medical or academic records), or video recordings.

- **Examples**: survey, questionnaires, subject logs or diaries, focus group questions.
- **NOTE:** Sometimes the IRB can approve the general content of surveys and other data collection instruments rather than the specific form itself. This prevents the need to submit a modification request for future minor changes that do not add new topics or increase the sensitivity of the questions. To request this general approval, use the text box below to identify the questionnaires/surveys/ etc. for which you are seeking this more general approval. Then briefly describe the scope of the topics that will be covered and the most personal and sensitive questions. The HSD staff person who screens this application will let you know whether this is sufficient or whether you will need to provide more information.
- For materials that cannot be uploaded: upload screenshots or written descriptions that are sufficient to enable the IRB to understand the types of data that will be collected and the nature of the experience for the participant. You may also provide URLs (website addresses) or written descriptions below. Examples of materials that usually cannot be uploaded: mobile apps; computer-administered test; licensed and restricted standardized tests.
- For data that will be gathered in an evolving way: This refers to data collection/questions that are not pre-determined but rather are shaped during interactions with participants in response to observations and responses made during those interactions. If this applies to the proposed research, provide a description of the process by which the data collection/questions will be established during the interactions with subjects, how the data collection/questions will be documented, the topics likely to be addressed, the most sensitive type of information likely to be gathered, and the limitations (if any) on topics that will be raised or pursued.

Use this text box (if desired) to provide:

- Short written descriptions of materials that cannot be uploaded, such as URLs
- A description of the process that will be used for data that will be gathered in an evolving way.
- The general content of questionnaires, surveys and similar instruments for which general approval is being sought. (See the **NOTE** bullet point in the instructions above.)

6.1)Involvement of minors. Does the research include minors (children)?

Minor or child means someone who has not yet attained the legal age for consent for the research procedures, as described in the applicable laws of the jurisdiction in which the research will be conducted. This may or may not be the same as the definition used by funding agencies such as the National Institutes of Health.

- In Washington State the generic age of consent is 18, meaning that anyone under the age of 18 is considered a child.
- There are some procedures for which the age of consent is much lower in Washington State.
- The generic age of consent may be different in other states, and in other countries.

 \rightarrow If no, go to Section 8.

	If yes, provide the age range of the minor subjute study population(s). If there is more than a		ge for consent in			
Children ages 12-36 months. Due to their young age, parental permission will be sought and consent and permission will be provided by a legal caregiver over 18 years of age.						
Don't kno	 →This means is it not possible to know the for some research involving social means another researcher or from a governmean to the source of t	lia, the Internet, or a dataset tha				
same as "passiv participate bec	ssion. Parental permission means actively obta ve" or "opt out" permission where it is assume ause they have been provided with information n indicating they don't want their children to p	d that parents are allowing their n about the research and have no	children to			
a. Will parenta	l permission be obtained for:					
X All of the	research procedures \rightarrow Go to questi	on 6.2b.				
None of t	the research procedures \rightarrow Use the table 6.2b.	→ Use the table below to provide justification, and skip question 6.2b.				
Some of t	Some of the research procedures Some of the research procedures for which parental permission will not be obtained.					
Be sure to consic specimens for fu	der all research procedures and plans, including scre ture work.	ening, future contact, and sharing/b	anking of data and			
Children Group ¹	Describe the procedures or data/specimen collection (if any) for	Reason why parental permission will not be	Will parents be			
	which there will be NO parental permission ²	obtained	informed about the research? ³ YES NO			
		obtained	the research? ³			
		obtained	the research? ³			
		obtained	the research? ³			
		obtained	the research? ³			
		obtained	the research? ³			

Table footnotes

- 1. If the answer is the same for all children groups or all procedures: collapse the answer across the groups and/or procedures.
- 2. If identifiable information or biospecimens will be obtained without parent permission, any waiver granted by the IRB does not override parents' refusal to provide broad consent (for example, through the Northwest Biotrust).
- 3. Will parents be informed about the research beforehand even though active permission is not being obtained?

b. Indicate the plan for obtaining parental permission. One or both boxes must be checked.

Both parents, unless one parent is deceased, unknown, incompetent, or not reasonably available; or when only one parent has legal responsibility for the care and custody of the child

One parent, even if the other parent is alive, known, competent, reasonably available, and shares legal responsibility for the care and custody of the child.

This is all that is required for minimal risk research.

If both boxes are checked, explain:

6.3 Children who are wards. Will any of the children be wards of the State or any other agency, institution, or entity?

→ If yes, an advocate may need to be appointed for each child who is a ward. The advocate must be in addition to any other individual acting on behalf of the child as guardian or in loco parentis. The same individual can serve as advocate for all children who are wards.

Describe who will be the advocate(s). The description must address the following points:

- Background and experience
- Willingness to act in the best interests of the child for the duration of the research
- Independence of the research, research team, and any guardian organization

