Subject units mean units within a group. For most research studies, a group will consist of individuals. However, the unit of interest in some research is not the individual. Examples:

- Dyads such as caregiver-and-Alzheimer's patient, or parent and child
- Families

No

• Other units, such as student-parent-teacher

Subject group means categories of subjects that are meaningful for the specific study. Some research has only one subject group – for example, all UW students taking Introductory Psychology. Some common ways in which subjects are grouped include:

- By intervention for example, an intervention group and a control group.
- By subject population or setting for example, urban versus rural families
- By age for example, children who are 6, 10, or 14 years old.

The IRB reviews the number of subjects in the context of risks and benefits. Unless otherwise specified, if the IRB determines that the research involves no more than minimal risk: there are no restrictions on the total number of subjects that may be enrolled. If the research involves more than minimal risk: The number of enrolled subjects must be limited to the number described in this application. If it is necessary later to increase the number of subjects, submit a Modification. Exceeding the IRB-approved number (over-enrollment) will be considered non-compliance.

→ If no, provide the rationale in the box below. Also, provide any other available information about the scope/size of the research. You do not need to complete the table.

Example: It may not be possible to predict the number of subjects who will complete an online survey advertised through Craigslist, but you can state that the survey will be posted for two weeks and the number who respond is the number who will be in the study.

X Yes → If yes, for each subject group, use the table below to provide the estimate of the maximum desired number of individuals (or other subject unit, such as families) who will complete the research.

Group name/description	Maximum desired number of individuals (or other subject unit, such as families) who will complete the research Provide numbers for the site(s) reviewed by the UW IRB and for the study-wide total number; example: 20/100
Children with CP or at risk for CP	18
Parent/Legal Guardian	18

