3 NON-UW RESEARCH SETTING

Complete this section only if UW investigators and people named in the SUPPLEMENT: Non-UW Individual Investigators will conduct research procedures outside of UW and Harborview

3.1 Reason for locations. Describe the reason(s) for choosing the locations.

This is especially important when the research will occur in locations or with populations that may be vulnerable to exploitation. One of the three ethical principles the IRB must consider is justice: ensuring that reasonable, non-exploitative, and well-considered procedures are administered fairly, with a fair distribution of costs and potential benefits.

This study is a multi-site collaboration which involves two additional co-investigators and research sites: [name] at Oregon State University, and [name] at Grand Valley State University. These locations have been selected due to an ongoing collaborative relationship with Drs. [name] and [name], who, together with [name] from UW have a history of research collaboration and publication in the field of early powered mobility for children with disabilities. This project allows for a diverse demographic and geographic study sample which will strengthen the rigor of our work.

3.2Local context. Culturally appropriate procedures and an understanding of local context are an important part of protecting subjects. Describe any site-specific cultural issues, customs, beliefs, or values that may affect the research, how it is conducted, or how consent is obtained or documented.

Examples: It would be culturally inappropriate in some international settings for a woman to be directly contacted by a male researcher; instead, the researcher may need to ask a male family member for permission before the woman can be approached. It may be appropriate to obtain permission from community leaders prior to obtaining consent from individual members of a group. In some distinct cultural groups, signing forms may not be the norm.

This federal site maintains an international list of human research standards and requirements: http://www.hhs.gov/ohrp/international/index.html

APPLICATION IRB Protocol

We do not anticipate any site-specific cultural issues to impact this work.

3.3Location-specific laws. Describe any local laws that may affect the research (especially the research design and consent procedures). The most common examples are laws about:

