Research Design and Timeline: We will conduct our work using a mixed-methods, counterbalanced AB crossover design, where intervention A is use of the Explorer Mini, and intervention B is use of the modified ride-on car. All participants at all sites will undergo the same research procedures. Participants will receive both powered mobility interventions, and randomization into two groups at each site will occur to determine which intervention participants will receive first (Modified ride-on car: n = 3; Explorer Mini: n = 3). Three research visits will be scheduled during the study. Baseline assessment (T0) will consist of initial device training and safety checkoff, interview, and administration of outcome measures. Intervention phase 1 will take place for 8 weeks, followed by a mid-study assessment (T1) at which time interviews and outcome measures will be repeated and parent perception/satisfaction with device will be assessed. Training and safety checkoff on the second device will occur. No washout period between devices is indicated because both devices provide self-initiated mobility. Intervention phase 2 will take place for 8 weeks, followed by the final study assessments (T2), where devices will be removed from the participants' homes and a final set of interviews and outcome measures will be administered. During each 8-week study phase, the researchers will conduct two virtual check-ins with each family to answer questions and provide support and standard activity suggestions for device use (i.e. open exploration, switch/joystick play, goal-directed driving).

Equipment:

Modified Ride-On Cars. Commercially available, off-the-shelf, battery-operated rideon toy cars will be modified. *Switch activation*. Unmodified, a child uses their foot to press a pedal or their finger to press a small switch located on the steering wheel to activate the ride-on car which is difficult for young children with CP. Modifications of ride-on cars will include installation of an easy-to-press switch that has a large surface area and responds to a light touch for activation. *Seating support*. Common materials, such as PVC pipe, swimming kickboards, and Velcro will be used to build a

customized supportive seating system. Seatbelts are added in all cars, and fivepoint harnesses are available if needed for appropriate postural support. Cars

Figure 1. Child with CP using a modified ride-on car.

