ID: STUDY00011386 Early Powered Mobility for Toddlers With Cerebral Palsy Using the Permobil® Explorer Mini and a Modified Ride-On Car

Statistical Analysis Plan Document Date: 12/1/2020

Statistical Design and Power

Data Analysis:

All statistical analyses will be conducted using SPSS (version 26.0 IBM, Armonk, NY). Descriptive participant characteristics (e.g., age, sex, race/ethnicity, CP subtype, GMFCS-level) will be summarized as categorical variables.

Aim 1: Developmental, activity and participation outcomes

Sample size justification: Since the current proposal is a pilot study, there are no previous data to conduct a power analysis on the potential change of developmental, activity and participation outcomes as a result of using different powered mobility devices.

Analysis for measures assessed in Aim 1 will include descriptive statistics. Data will be assessed for normality and symmetry. If normality assumptions are met, we will use parametric statistics to examine between- and within-subject effects. If assumptions are not met, we will use the non-parametric equivalent of the planned analyses. We will calculate three separate analyses to examine changes in_developmental, activity and participation outcomes. (1) Separate 2 (group: 1, 2) x 3 (time: T0, T1, T2) repeated measures MANOVAs will be calculated to determine between- and within-subject changes on mean scores of developmental, activity and participation outcomes. (2)_Stratification into low and high usage groups will occur based on mean device use data. We will use these stratified groups to run our analyses to determine if device use is related to developmental, activity and participation outcomes. Separate 2 (group: low usage, high usage) x 3 (time: T0, T1, T2) repeated measures MANOVAs will be calculated to determine between- and scores of developmental, activity and participation outcomes. Separate 2 (group: low usage, high usage) x 3 (time: T0, T1, T2) repeated measures MANOVAs will be calculated to determine between- and within-subject changes on mean scores of developmental, activity and participation outcomes. Post-hoc analyses (i.e. Bonferonni correction) will be used for the above analyses to control for the type I error rate and determine where the significant differences exist. (3) We will also use visual analysis to determine if clinically significant differences exist.

Aim 2: Use patterns (frequency, duration, environment) & families' perspective and experiences

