Sample size justification: A power analysis based on preliminary data was used to determine the number of participants (*N*) necessary to satisfy statistical assumptions for the current study. Power was calculated from the results of the total time (minutes) a modified ride-on car was used between two groups: (1) Families who received bi-weekly support via in-person researcher visits (Mean minutes = 1,060; SD = 783.8), and (2) Families who received no support throughout a 3-month intervention period (Mean minutes = 171.4; SD = 206.1). Beta was set at .80 and alpha at .05 to calculate *N* which is standard practice. Analysis indicates that a sample of 6 participants in each group (modified ride-on cars, Explorer Mini) will produce meaningful treatment differences. This power analysis is appropriate given our hypothesis that the Explorer Mini will be used more frequently and more often than a modified ride-on car based on design features. Also, the above power analysis from previous data is based on between-group differences whereas the current study will examine within-group differences of use patterns between devices, resulting in less variability and greater likelihood of observing differences, if differences exist.

95% confidence intervals and mean number of driving sessions, mean duration (minutes) of driving sessions, and summed total duration (minutes) of driving sessions will be summarized by device type. Variable distributions will be examined to (1) identify appropriate response variable distributions, (2) screen for outliers, and (3) characterize patterns of data missingness. If assumptions for parametric statistics are met, we will use parametric statistics to examine within-subject effects. If assumptions for parametric statistics are not met, we will use the non-parametric equivalent of the planned analyses. A 2

(group: 1, 2) x 2 (time: T1, T2) repeated measures MANOVA will be calculated to determine withinsubject changes on the dependent measures of the mean number of driving sessions, mean duration (minutes) of driving sessions, and summed total duration (minutes) of device use. Significant differences will be followed-up with appropriate post-hoc analyses such as the Bonferonni correction to control for the type I error rate and determine where the significant differences exist.

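### Device order is randomised within three sites, but no SAP model includes site: between-child sequence tests lose power if sites differ, and the low/high usage comparison is open to site confounding

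*Protocol*

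**What the plan says.** Protocol section 5.1 (Research Design and Timeline) describes a two-period crossover in which "randomization into two groups at each site will occur to determine which intervention participants will receive first", with the allocation given as "Modified ride-on car: n = 3; Explorer Mini: n = 3". Section 3.1 calls the study a "multi-site collaboration which involves two additional co-investigators and research sites", so there are three sites with the lead university. In section 2.7 the row "Children with CP or at risk for CP" shows 18, which is 3 sites × 6 children, or 9 per order.

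The SAP names three models and no stratification factor or covariate:

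- **Aim 1, randomised:** sequence group × time (T0, T1, T2), where "repeated measures MANOVAs will be calculated to determine between- and within-subject changes on mean scores of developmental, activity and participation outcomes".
- **Aim 1, usage:** the same structure, with children split into low and high users on observed device use.
- **Aim 2:** the model "group: 1, 2) x 2 (time: T1, T2) repeated measures MANOVA", applied to three device-use measures and described as within-subject.

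On how far sites may differ, the protocol points both ways. Section 5.1 says "All participants at all sites will undergo the same research procedures". Section 3.1 says "This project allows for a diverse demographic and geographic study sample which will strengthen the rigor of our work".

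**The concern.** The analysis should follow the randomisation. When sequence groups are balanced within sites, site differences drop out of the group comparison. If site is left out of the model, its variance still sits in the error term. The test is then too cautious, and in a trial of 18 children the lost power matters.

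The usage analysis raises a different and more serious problem. Low and high users are not randomised, so nothing balances them across sites. If one site has both heavier use and higher scores for unrelated reasons, the comparison can read as more use leading to better development.

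The SAP's own pilot figures show that device use can move a great deal with researcher support: a mean of 1,060 minutes with regular visits against 171.4 with none. Support in this trial comes from research teams at three institutions.

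**Working it through.** **The plan's own figure.** The only sample-size calculation (SAP, Aim 2) does not involve site. The difference is 1,060 − 171.4 = 888.6. The pooled SD is √[(783.8² + 206.1²)/2] = 573.1, so d = 1.55. The one-sided normal formula gives 2(1.645 + 0.842)²/1.55² ≈ 5.1, rounded up to 6 per group, as stated. The two-sided version gives 7, or 8 with the t-test. This point does not change that figure.

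**Inputs.** Three sites with 3 + 3 children each come from the protocol. Tests are taken as two-sided at 5%. The site ICC, meaning the share of score variance lying between sites, is not in the documents, so it is an assumption and is varied from 0 to 0.5.

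**1. Between-child sequence test.** Let τ² be the site variance and σ² the within-site variance, with τ² + σ² = 1.

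- The variance of the group difference is σ²(1/9 + 1/9). Site cancels because each site is 3:3.
- The expected error mean square without site is [14σ² + 2(σ² + 6τ²)]/16 = σ² + 0.75τ². With site it is σ².
- ICC 0.2: 0.80 + 0.15 = 0.95, so the ratio is 0.95/0.80 = 1.19 and the standard error is 9% too large.
- ICC 0.3: 0.70 + 0.225 = 0.925, so the ratio is 0.925/0.70 = 1.32 and the standard error is 15% too large.

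Simulation (100,000 runs, effect of 1.4 within-site SDs for power; ranges show repeat runs):

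| Site ICC | Type I error, no site | Type I error, with site | Power, no site | Power, with site |
|---|---|---|---|---|
| 0 | 5.1% | 5.0% | 80% | 79% |
| 0.1 | 4.3% | 5.0% | 77% | 79% |
| 0.2 | 3.6% | 5.0% | 74% | 78–79% |
| 0.3 | 3.0–3.1% | 5.1% | 70% | 79% |
| 0.5 | 2.0% | 5.1% | 59% | 79% |

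**2. Within-child device contrast (group × period).** The outcome is the difference between a child's two periods, so a constant site effect subtracts out. Type I error was 4.9 to 5.0% with or without site, even with large site effects. If site-by-period differences make up 10%, 20% or 30% of the variance of that difference, type I error without site is 4.3%, 3.6% or 3.0%, again conservative.

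**3. Low/high usage groups.** Use was split at its mean. Site acted separately on use and on score with equal ICC, and there was no true link within site (20,000 runs per setting; ranges show repeat runs).

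| Site ICC (use and score) | Score level, no site | Score level, with site | T0-to-T2 change, no site |
|---|---|---|---|
| 0.1 | 5.2–5.4% | about 5% | 4.9% |
| 0.2 | 6.1–6.4% | about 5% | 5.0–5.1% |
| 0.3 | 7.7–8.2% | about 5% | 4.8–4.9% |
| 0.5 | 14.1–14.7% | about 5% | 4.9–5.2% |

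If site affects score but not use (score ICC 0.3), the rate without site is 4.7%. Confounding therefore needs site to act on both. For the usage × time term, it needs site to affect use and the rate of change.

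**4. Cost of adding site.** For a two-group multivariate test of p responses, the denominator degrees of freedom fall from 17 − p to 15 − p. Start from 80% power with no site effect and hold the noncentrality fixed:

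| Responses tested jointly | Denominator df | Power with site |
|---|---|---|
| 1 | 16 → 14 | 79.2% |
| 3 | 14 → 12 | 77.9% |
| 5 | 12 → 10 | 76.1% |
| 10 | 7 → 5 | 65.1% |

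**The case against.** A reader might infer that every randomised test in the SAP is mis-calibrated. The documents do not support that. The informative randomised effects in a crossover are within-child: the Aim 2 device contrast and the Aim 1 group × time terms. Constant site differences cancel in both. Where the randomised analysis is affected, the error is towards caution, so no false positive follows from it.

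A reader might also infer that the usage × time result is inflated by any site difference. It is not. The plan includes a baseline, and for change from T0 the rate stays at about 5% under constant site effects. The inflation shown applies to the usage-group main effect, and reaches usage × time only if sites also differ in rate of change.

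Three further objections carry weight:

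- **Site variance is unknown.** Procedures are common to all sites, Bayley sessions are filmed and scored later, and the participation surveys are completed remotely by caregivers. All of this may keep site effects small, and at ICC 0.1 the usage inflation is negligible. Common procedures do not make families, settings or staff the same, however, and central scoring across sites is not stated. The pilot contrast in support is also wider than anything planned here, so it shows that use responds to support, not that sites will differ.
- **The adjustment is not free.** The SAP specifies MANOVAs and does not say how many scores enter each Aim 1 model. With many responses tested jointly, the loss is large.
- **This is a pilot.** That lowers the stakes of lost power. It matters less for the usage analysis, because protocol section 5.10 expects the data to feed later grant applications.

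**Conclusion.** The point holds in a limited form. The trial randomises within site and the SAP never analyses by site.

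For the Aim 1 between-child sequence tests, the consequence is a conservative test and a loss of roughly 4 to 9 points of power at site ICC 0.2 to 0.3. For the low/high usage comparison, it is a possible false finding, with an error rate of about 6% to 8% at ICC 0.2 to 0.3 and 14% at 0.5. The second is the more important, because it can create a result rather than hide one. The Aim 2 device contrast and the group × time terms are affected only by site-by-period or site-by-time differences.

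All sizes rest on an assumed ICC and on single-outcome simulations of what will be multivariate tests. They show direction and rough size, not a forecast for this trial. The omission itself is plain from the documents.

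**What to change.** Amend the SAP before results are seen:

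1. **Priority:** add site (three levels, fixed main effect, no group × site term) to the low/high usage analyses, with site × time wherever change over time is tested. Tabulate usage group by site. If a site is nearly all low or all high users, report that use and site cannot be separated there.
2. Add site in the same way to the Aim 1 between-child sequence-group tests.
3. Where the non-parametric route is taken, stratify the rank or permutation test by site.
4. For the Aim 2 within-child device contrast, site is optional, as a sensitivity analysis.

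No new data are needed. The price is 2 of 16 error degrees of freedom. If sites do not differ, the loss from 80% power is about 1 point for one outcome, 2 for three, 4 for five and 15 for ten tested jointly. Apply the adjustment per outcome or to small outcome sets, and state in the SAP which scores enter each model.
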